10.2.2. Impact of the treatment chosen on the cold symptoms' duration

Hereinafter, the “recovery date” is the first day of two last days the patient answered to the WURSS-K questionnaire. The patient must have reported a negative answer to the question 1 (“not sick”) and the two last days must be consecutive. Otherwise, there is no “recovery date” for the patient.

For the items 2 to 7 of WURSS-K questionnaire, the duration of the corresponding symptom is defined as the duration between first symptomatic day and last symptomatic day.

Cold symptom's duration (days) = Last symptomatic day – first symptomatic day + 1

For a given symptom, a symptomatic day is a day the patient gave an answer other than negative to the corresponding question (“do not have this”). Missing answers will be imputed by the last observation carried forward (LOCF).

The considered symptomatic days are between D1 and either D30, or the end of the study, or the day before the recovery date, whichever occurs first. Symptomatic days from the recovery date will not be taken into account.

For each of the items 2 to 7 of the WURSS-K questionnaire, the origin date will be the date of the first symptomatic day.

The considered event is the end of the symptom.

For patients who reported a negative answer to the corresponding question on the last day they answered to it, or for patients with a recovery date, the event date will be the last symptomatic day before his/her last day of completion of the questionnaire, or before the recovery date if it exists.

Patients who did not report a negative answer to the corresponding question on the last day they answered to it, and without recovery date, will be censored at D30 or at the end of the study, and the censoring date will be the date of D30 or the reference end date, whichever occurs first.

For patients who never reported the presence of a given symptom (never ticked “a little bad”, “bad” or “very bad”), if they completed the questionnaire at D1, then their origin date will be D1, they will be censored at D1 and their corresponding duration will be zero, else they will have neither origin date nor censoring date and the corresponding duration will be missing.

For each of the items 2 to 7 of the WURSS-K questionnaire, the impact of the treatment chosen on the corresponding cold symptom' duration will be analysed by means of a Cox model. Subjects will be analysed on the FAS.

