XXXXX	XX (XX.X%)	XX (XX.X%)	XX (XX.X%)
XXXXX	XX (XX.X%)	XX (XX.X%)	XX (XX.X%)

Table 14.1.2.4. Symptoms of acute infectious rhinitis at baseline – Full Analysis Set

	Healsea Children N=XX	Conventional therapy N=XX	Total N=XX
Temperature (°C)			
N	XX	XX	XX
Missing	XX	XX	XX
Mean (SD)	XX.X (XX.X)	XX.X (XX.X)	XX.X (XX.X)
Median	XX	XX	XX
Q1/Q3	XX / XX	XX / XX	XX / XX
Min/Max	XX / XX	XX / XX	XX / XX
Between-groups test	XXX (Student/Wilcoxon)		
XXXXX score			
N	XX	XX	XX
Missing	XX	XX	XX
Mean (SD)	XX.X (XX.X)	XX.X (XX.X)	XX.X (XX.X)
Median	XX	XX	XX
Q1/Q3	XX / XX	XX / XX	XX / XX
Min/Max	XX / XX	XX / XX	XX / XX
Between-groups test	XXX (Student/Wilcoxon)		
Total score			
N	XX	XX	XX
Missing	XX	XX	XX
Mean (SD)	XX.X (XX.X)	XX.X (XX.X)	XX.X (XX.X)
Median	XX	XX	XX
Q1/Q3	XX / XX	XX / XX	XX / XX
Min/Max	XX / XX	XX / XX	XX / XX
Between-groups test	XXX (Student/Wilcoxon)		

Table 14.1.3. Summary of compliance on Healsea Children arm – Full Analysis Set

	Healsea Children N=XX
Compliance (%)	
N	XX
Missing	XX
Mean (SD)	XX.X (XX.X)
Median	XX
Q1/Q3	XX / XX
Min/Max	XX / XX

Table 14.1.4. Study duration by subject – Full Analysis Set

	Healsea Children N=XX	Conventional therapy N=XX	Total N=XX
Study duration (days)			
N	XX	XX	XX
Missing	XX	XX	XX
Mean (SD)	XX.X (XX.X)	XX.X (XX.X)	XX.X (XX.X)
Median	XX	XX	XX
Q1/Q3	XX / XX	XX / XX	XX / XX
Min/Max	XX / XX	XX / XX	XX / XX

Table 14.2.1.2. Global AUC on total WURSS per treatment group – Per-Protocol Set

	Healsea Children N=XX	Conventional therapy N=XX	Total N=XX
Global AUC on total WURSS			
N	XX	XX	XX
Missing	XX	XX	XX
Mean (SD)	XX.X (XX.X)	XX.X (XX.X)	XX.X (XX.X)
Median	XX	XX	XX
Q1/Q3	XX / XX	XX / XX	XX / XX
Min/Max	XX / XX	XX / XX	XX / XX
Between-groups test	XXX (Student/Wilcoxon)		

Table 14.2.2.1.2. Modelling of AUC on total WURSS by multivariate ANCOVA – Per-Protocol Set

	Healsea Children N=XX	Conventional therapy N=XX
Global AUC on total WURSS		
ANCOVA model :		
AUC = Treatment + ...		
Type 3 Tests of Fixed Effects		
Treatment	XXX	
...	XXX	
Adjusted mean		
LSMeans (SE)	XX.X (XX.X)	XX.X (XX.X)
[LSM 95%CI]	[XX.X; XX.X]	[XX.X; XX.X]
Adjusted mean (diff. vs Conventional therapy)		
LSMeans (SE)	XX.X (XX.X)	
[LSM 95%CI]	[XX.X; XX.X]	
Contrast vs Conventional therapy, p=	XXX	

Table 14.2.2.2. Impact of the treatment chosen on the cold symptoms' duration – Full Analysis Set

	Healsea Children N=XX	Conventional therapy N=XX
XXX – Duration (days)		
N	XX	XX
Missing	XX	XX
Mean (SD)	XX.X (XX.X)	XX.X (XX.X)
Median	XX	XX

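### The symptom-duration table puts zeros for never-symptomatic children, and censored times, into its plain summaries, while the hazard ratio beside them covers only children who had the symptom

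*SAP*

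**What the plan says.** SAP 10.2.2 defines duration separately for WURSS-K items 2 to 7:

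- **Children who reported the symptom.** "Cold symptom's duration (days) = Last symptomatic day – first symptomatic day + 1". For the Cox model "the origin date will be the date of the first symptomatic day", and "The considered event is the end of the symptom".
- **Children whose symptom had not resolved and who have no recovery date.** They are censored, and "the censoring date will be the date of D30 or the reference end date, whichever occurs first".
- **Children who never reported the symptom but completed D1.** Their origin is D1, and "they will be censored at D1 and their corresponding duration will be zero".
- **Children who never reported the symptom and did not complete D1.** "else they will have neither origin date nor censoring date and the corresponding duration will be missing".

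The results go into mock Table 14.2.2.2 (SAP 13.2), titled "Impact of the treatment chosen on the cold symptoms' duration". Per group it lists N, Missing, Mean (SD), Median, Q1/Q3 and Min/Max of duration in days, followed by the hazard ratio with 95% CI and a Wald p-value. It has no row for never-symptomatic children, events or censored children, and no Kaplan-Meier estimate. Neither 10.2.2 nor SAP section 12 limits the descriptive rows to children who had the symptom or adjusts them for censoring.

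**The concern.** The two halves of the table describe different children. The hazard ratio compares how quickly the symptom ends among those who had it. The mean, median and quartiles also absorb the share who never had it, entered as zero days, and they treat unfinished durations as finished.

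A reader will take a difference in mean days as longer or shorter symptoms. It may only reflect how many children in each group ever ticked the symptom. Zeros are to be expected: inclusion criterion 6 asks for just one of sore throat, runny nose or blocked nose, while the table covers six items, including cough, sneezing and tiredness. Families choose the group (Protocol 8.2), so nothing in the design balances symptom profiles.

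**Working it through.** **The plan's own figure.** The documents give no figure for the duration analysis. The only design figure is 100 per group for the AUC (SAP section 4). With d = 0.4, 80% power and two-sided 5%, n = 2 × (1.960 + 0.842)² / 0.4² = 98.1, so 99 per group; power at 100 per group is 80.7%. That figure reproduces, and 100 per group is used below.

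**Step 1: who enters which calculation.** The formula gives a symptomatic child at least 1 day, since last day equals first day at the shortest. A child censored at time 0 has left before the first possible event time. In one simulated data set (geometric durations, censoring at 30 days, 40% against 20% never symptomatic), the Cox fit was the same with and without the zeros: HR 0.870, SE 0.1751, p = 0.426 both times. The descriptive rows exclude only missing values, so the zeros stay in.

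**Step 2: what the printed mean is.** With p the share never symptomatic and m the mean among symptomatic children, table mean = (1 − p) × m. If m is equal in both groups, the gap is m times the difference in p: each 10 percentage points moves the means apart by 0.5 days at m = 5 and 0.7 days at m = 7. All p and m below are assumptions.

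| Never symptomatic, Healsea vs conventional | True mean days if symptomatic | Printed mean | HR for symptom end (simulated) |
|---|---|---|---|
| 20% vs 20% | 7 vs 7 | 5.6 vs 5.6 | about 1.0 |
| 30% vs 20% | 5 vs 5 | 3.5 vs 4.0 | about 1.0 |
| 40% vs 20% | 5 vs 5 | 3.0 vs 4.0 | about 1.0 |
| 30% vs 20% | 7 vs 7 | 4.9 vs 5.6 | about 1.0 |
| 40% vs 20% | 7 vs 7 | 4.2 vs 5.6 | about 1.0 |
| 20% vs 40% | 6 vs 7 | 4.8 vs 4.2 | about 1.19 |

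Simulated means agree to within about 0.1 day; the small shortfall comes from stopping at day 30. In the last row the hazard ratio favours Healsea while the printed mean favours conventional therapy. Restricted to symptomatic children, the simulated means there are 6.0 against 7.0 days, in line with the hazard ratio.

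**Step 3: median and quartiles.** Once more than 25% of a group are zeros, Q1 is 0 whatever the duration among symptomatic children. Above 50%, so is the median.

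**Step 4: censored times.** The SAP does not say which value a censored child contributes to the descriptive rows: the formula uses the last symptomatic day, while the censoring date is D30 or the reference end date. If 10% were carried to day 30 and the rest averaged 7 days, the mean would be 0.9 × 7 + 0.1 × 30 = 9.3 days. In the other direction, when simulated children stopped the diary early and contributed only the time to that point, the mean fell from 6.9 to 6.4 days with 8.4% censored. Nothing in the table would show either.

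**Step 5: the +1 day rule.** SAP 6.4.2 gives a general rule of later date minus earlier date plus 1 day. Applied to origin D1 and censoring D1, it gives 1 rather than 0, and these children then join the first risk set. In the Step 1 data the HR becomes 0.837 instead of 0.870. The explicit zero in 10.2.2 points against this, but the SAP does not state the exception.

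**The case against.** **Zero fits the protocol's definition.** Protocol 8.1.4 counts symptomatic days from D1, and a child who never has the symptom has none. Restricting to children who reported it conditions on something that happens after the treatment choice and changes the quantity. This stands. A mean over all children is a legitimate summary if labelled as days with the symptom; what fails is printing it, unlabelled, as the duration that belongs with the hazard ratio.

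**The treatment estimate is sound, and the endpoint is descriptive.** SAP 6.3.1 reserves conclusions for the primary criterion. This stands too, and limits the consequence. But if the results are to be read descriptively, the descriptive rows carry more of the weight.

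**The imbalance is assumed.** True: the shares are put in by hand, and with equal shares there is no gap.

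**Censoring may be rare, because a recovery date turns every item into an event.** That limits the second part of the problem, but without a count of censored children the reader cannot tell.

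**Baseline symptom scores are already tabulated by group and are candidate covariates (SAP 8.4 and 10.2).** This helps in part. They cover five of the six items, not tiredness, and describe entry rather than the whole diary. The printed means are unadjusted.

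A reader might go further and infer that a difference in zeros is a baseline imbalance. The documents do not support that. Zero requires never reporting the symptom at any time in the diary, which starts on the evening of D1, and the spray starts after Visit 1. The difference may be partly baseline and partly post-treatment.

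**Conclusion.** The point holds as a defect of one secondary table. Followed as written, SAP 10.2.2 and Table 14.2.2.2 would print summaries that mix occurrence with duration and treat censored times as complete, next to a hazard ratio that uses neither feature.

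Under the assumed shares, means differ by 0.5 to 1.0 day at a 5-day duration, or 0.7 to 1.4 days at 7 days, with no difference in duration; a reversal of direction is possible. The actual size is unknown because the documents give no shares, durations or censoring rates. The direction of the censoring bias is also open.

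Two readings are needed: that zeros enter the descriptive rows, inferred from a numeric zero and a shell that excludes only missing values; and that Cox time for symptomatic children is the stated duration of at least 1 day, with never-symptomatic children at time 0. It would be wrong to infer that the hazard ratio is biased by the zeros or that the AUC result is touched. Neither follows.

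**What to change.** For each of items 2 to 7 in Table 14.2.2.2, by group:

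- Add the number and percentage never symptomatic, with a confidence interval, and the numbers of events and censored.
- Give Kaplan-Meier median and quartiles among children who reported the symptom.
- State that the hazard ratio covers those children only, and that the +1 day rule in 6.4.2 is not applied to the zero times.
- If the mean and SD including zeros are kept, label them as days with the symptom over all children, say which value a censored child contributes, and do not present them as the duration that matches the hazard ratio.

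The cost is one table shell, its program and two or three sentences in 10.2.2. The downside is a few more rows. The comparison among symptomatic children also conditions on an event after the treatment choice, and a footnote should say so.

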8.1.4 Secondary Endpoints

- **Duration of cold symptoms** (items 2 to 7) will be assessed by means of the WURSS-K (assessed once daily in the evening).

During treatment period, the WURSS-K will be assessed once daily in the evening, taking in account the symptoms from the morning to the evening.

After D10, the WURSS-K will be assessed once daily until the subject feels not sick for two consecutive days.

For each item, the duration is defined as the number of symptomatic days between D1 and the first day the subject reports not having the symptom for two consecutive days.

To be noticed that the duration may be censored at day 30.

- Number of subjects who develop respiratory complication requiring antibiotic prescription during a 20-day follow-up period. Healsea® Children is expected to reduce acute rhinitis complications.
- Frequency and number of days of use of concomitant treatments that may affect common cold symptoms (antibiotics, antipyretics, mucolytics, decongestants, antitussives, systemic and topical

Version: **2.0**; **08** Sep **2021** Page **30** of **61** Study Number: **LPH-2101**

corticosteroids). By reducing duration of common cold symptoms, Healsea® Children will very likely reduce the use of common rescue medication.

- Number of family members in close contact developing common cold symptoms after the patient all over the study period. The daily use of Healsea® Children started at the onset of common cold symptoms is expected to reduce relative's contamination.
- Safety: Assessment of adverse events/incidents/undesirable expected side effects throughout the study.

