4. SAMPLE SIZE

An arbitrary cohort of 200 children has been chosen. A cohort of 100-exposed and 100-not exposed patients is anticipated to allow to demonstrate the interest of using Healsea® Children in the allergic paediatric population.

Indeed, 100 patients by arms are enough to detect a Cohen's effect size of 0.4 with a power of 80% and a type I error of 5%. Cohen's effect size is defined as the standardized difference between AUC in groups. Following Cohen's methodology, 0.4 is an intermediate size between a small effect (0.2) and a medium effect (0.5) and is coherent with the expected result.

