6. STATISTICAL METHODS

6.1. Data processing

The analyses will be computed with SAS Version 9.4 TS Level 1M6 Copyright (c) 2016 by SAS Institute Inc., Cary, NC, USA.

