6.3. Statistical/Analytical issues

6.3.1. Significance level

All statistical analyses will be performed at the 0.05 global significance level (type I error rate), using two-sided tests.

The statistical results are conclusive for the primary efficacy criterion.

All the other statistical results have to be considered within a descriptive perspective and not as inferential issues. No adjustment for Type I error is done. P-values of statistical tests will be provided for information only.

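### Whole-day symptom durations will give the six Cox models heavily tied event times, and no tie method is named; Breslow handling, if applied, would pull the hazard ratios toward 1.

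*SAP*

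**What the plan says.** SAP 10.2.2 treats the duration of each of items 2 to 7 of the WURSS-K as a time-to-event outcome and computes it as "Last symptomatic day – first symptomatic day + 1", a whole number of days. The data come from the evening diary. Protocol 8.1.4 has it completed once daily during treatment and adds: "After D10, the WURSS-K will be assessed once daily until the subject feels not sick for two consecutive days". No finer clock time is available to separate two children whose symptom ends on the same day.

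For each of the six items the SAP states that the "duration will be analysed by means of a Cox model. Subjects will be analysed on the FAS". Durations are censored at D30 or at the end of the study. A child who never reports the symptom, but completed the D1 questionnaire, is censored at D1 with duration zero.

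On software, SAP 6.1 says only: "The analyses will be computed with SAS Version 9.4 TS Level 1M6". No procedure or option is given. The mock Table 14.2.2.2 reports a hazard ratio, a 95% confidence interval and a Wald p-value, with no sensitivity analysis for ties. On size, SAP section 4 says: "A cohort of 100-exposed and 100-not exposed patients is anticipated".

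SAP 6.3.1 declares every result other than the primary one descriptive, with p-values for information only.

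**The concern.** The Cox partial likelihood assumes that events can be ordered in time. When many fall on the same day, an approximation or an exact calculation is needed, and the choice changes the estimate. The Breslow approximation keeps every child whose symptom ends that day in the risk set for all of that day's endings. This pulls the log hazard ratio toward zero when there is an effect. Enrolling more children with the same pattern of durations does not remove the shrinkage.

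At stake are the six hazard ratios for the first-listed secondary objective, symptom duration. Protocol 6.1 anticipates quicker recovery with the device. Leaving the method open also leaves a choice that could be made after the estimates are seen.

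**Working it through.** **1. The plan's own figure.** The documents give no number for the Cox models. Their one calculation is for the AUC: "100 patients by arms are enough to detect a Cohen's effect size of 0.4". SAP section 4 sets the power at 80% and alpha at 5%, and SAP 6.3.1 makes the test two-sided.

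- n per group = 2 × (1.960 + 0.842)² / 0.4² = 98.1, so 99.
- Power at 100: Φ(0.4 × √(100/2) − 1.960) = Φ(0.868) = 0.807 (0.804 from the t distribution).

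The figure is reproduced. It bears on the Cox models only by fixing the group size.

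**2. Are ties heavy?** Up to 200 endings fall on at most 30 values. The only duration in the documents is about 7-10 days for the whole illness (Protocol 6.6), not for each symptom. If all 200 children have the symptom, with assumed Weibull durations of shape 2 and median 6-7 days, about 8-26 endings fall on each of D2 to D10. Across the wider range of assumptions in step 4 the busiest day has about 17-50. If 100-140 children have the symptom, it has about 11-30. Ties are heavy in every case, but the count rests on the assumptions.

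**3. Why Breslow shrinks the estimate.** Take one day with r₁ and r₀ children at risk and d₁ and d₀ endings. The Breslow equation is

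d₁ = (d₁ + d₀) × r₁eᵇ / (r₁eᵇ + r₀), so eᵇ = (d₁/r₁) / (d₀/r₀) = p₁/p₀.

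It therefore estimates the ratio of daily probabilities. With proportional hazards in continuous time, 1 − p₁ = (1 − p₀)^HR. For a true HR of 1.5 (log 0.4055):

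| p₀ per day | p₁ = 1 − (1 − p₀)^1.5 | p₁/p₀ | log | shrinkage |
|---|---|---|---|---|
| 0.06 | 0.0886 | 1.477 | 0.390 | 3.8% |
| 0.10 | 0.1462 | 1.462 | 0.380 | 6.4% |
| 0.15 | 0.2163 | 1.442 | 0.366 | 9.7% |
| 0.20 | 0.2845 | 1.422 | 0.352 | 13.1% |
| 0.30 | 0.4143 | 1.381 | 0.323 | 20.4% |

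The shrinkage depends on the daily probability of ending, not on the number of children. With HR = 1, p₁ = p₀ and there is no bias.

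**4. Simulation.** Assumed, not in the documents: two equal groups, proportional-hazards Weibull durations rounded up to whole days, censoring at D30, HR 1.3-2.0, shape 1-2.5, reference median 4-10 days, 100-200 children with the symptom, no covariates. Shrinkage of the Breslow log hazard ratio relative to Efron:

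| Setting | Shrinkage |
|---|---|
| Shape 2, median 5-7 days | about 10-15% |
| Shape 1.5, median 5-7 days | about 7.5-12% |
| Shape 1-2.5, median 7-10 days | about 4-13% |
| Full range | about 4-20% |

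Against the fit to unrounded times, the full range is about 3-24%. Percentages are good to 1-2 points. Efron is close to the unrounded-time fit in most settings and up to about 4-5% low in the most heavily tied (shape 2.5, median 4-5 days).

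A fresh run at HR 1.5 (200 data sets per setting, 100 per group) agrees. Relative to Efron, shrinkage is 9.0% for shape 1.5 and 11.6% for shape 2 at median 6 days. Relative to unrounded times these become 9.6% and 12.7%. With 60 per group, shape 2 and median 6, it is again 11.6% relative to Efron.

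**5. Size in practice.** For 200 children, HR 1.5, shape 2 and median 6 days, the mean log hazard ratio is 0.411 with Efron and 0.363 with Breslow; the standard error is 0.145 with both.

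- Efron: HR = e^0.411 = 1.51; 95% interval e^(0.411 ± 1.96 × 0.145) = 1.14 to 2.00.
- Breslow: HR = e^0.363 = 1.44; 95% interval e^(0.363 ± 1.96 × 0.145) = 1.08 to 1.91.
- Difference: 0.048, which is 0.048/0.145 = 0.33 standard errors.

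**The case against.** The strongest reply is that the SAP does not choose Breslow. It leaves an option unstated, and the shrinkage arises only if the software applies that approximation. This stands: the default is an assumption about SAS, and the flaw in the document is an omission.

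A second reply is that the analysis is descriptive and no power is claimed for it. This also stands. A reader might infer from the simulations a material loss of power for a treatment claim. SAP 6.3.1 rules that out: only the primary AUC test is conclusive, and the sample size was set for that test alone. What survives concerns estimation. In a descriptive analysis the hazard ratio and its interval are the result, so an avoidable attenuation sits in the reported quantity itself.

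Third, the simulation simplifies the endpoint. SAP 10.2.2 measures from first to last symptomatic day across gaps, carries the last observation forward and stops at a recovery date, and SAP 10.2 adds baseline covariates. These features could raise or lower the number of ties, so no single percentage can be claimed for all six symptoms. Children who never have a symptom contribute no event. That lowers the event count, but by step 3 it does not in itself change the shrinkage.

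Finally, the shift is small: for HR 1.5 typically 0.02-0.07 on the log scale, about 0.2-0.5 standard errors. In an open-label cohort where families choose their group, confounding is the larger threat.

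**Conclusion.** The point holds as a minor one. Whole-day durations make heavy ties a consequence of the design, and no tie method is named. If Breslow handling is applied, the log hazard ratio is attenuated by roughly 4-20%, and by about 9-13% for a median of 6 days with Weibull shape 1.5-2. Efron stays within about 0-5%. These figures rest on an assumed duration distribution, an assumed true hazard ratio and an assumed software default.

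A reader might infer that the plan will distort all six hazard ratios by one known amount, or that it contains a systematic error. The documents support neither: they give no per-symptom distribution, no tie count and no expected hazard ratio, and they do not select Breslow. The bias runs toward no difference and is absent under no effect, so it cannot create a false claim of benefit. The cost is understated hazard ratios, and intervals shifted with them, in a secondary descriptive analysis.

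**What to change.** Add to SAP 10.2.2, for each of the six models: *Ties are handled by the Efron method (TIES=EFRON), with the exact method as a check.* The exact check covers the most heavily tied settings, where Efron itself is slightly low.

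The cost is one sentence and one option in the code. The data collected, the endpoint definition and the sample size do not change. SAP section 12 shows that the definition of this endpoint has already been revised in view of the children's answers, so the tie method should be fixed in writing before the models are run.
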